#### 6.1.8.11 RENAL TOXICITY

Renal toxicity of pomalidomide is rare. Renal toxicity is defined by CTCAE version 4.0 criteria. An increase of creatinine of  $> 0.3$  mg/dl, or a baseline creatinine  $> 1.5$  with an increase at least 2x above baseline define Grade 1 nephrotoxicity. If these abnormalities are confirmed, the pomalidomide dose should be reduced to 3 mg/day. For higher levels of nephrotoxicity, the drug will be discontinued until the abnormalities have resolved and pomalidomide will then be reintroduced at a dose of 3.0 mg/day.

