#### 6.1.2 FORMULATION, APPEARANCE, PACKAGING AND LABELING

Pomalidomide or matching placebo will be supplied as 4.0 mg capsules for oral administration. Capsules of 3.0 and 2.0 mg pomalidomide or matching placebo will also be provided for patients who experience hematologic toxicity, fatigue or muscle cramping thought to be drug related, per guidelines described in Section 6.1.8. The new dose may be initiated after the unused capsules from the previous dose are collected.

Pomalidomide is dispensed to research subjects as individual bottles containing capsules. Each bottle will identify the contents as study medication. It is suggested as a component of the pomalidomide REMS program that patients not open or extensively handle pomalidomide capsules. All bottles will contain the following warning label: "WARNING: POTENTIAL FOR HUMAN BIRTH DEFECTS."

Placebo will contain Microcrystalline Cellulose (Type PH-102) (Compendia: NF, Ph Eur, JP) and the Swedish Orange (6180) Opaque Global Capsule Shell (Coni-Snap). Placebo will be indistinguishable from pomalidomide.

---

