#### 6.1.8 DOSE ADJUSTMENTS/MODIFICATIONS/DELAYS

Study drug dose may be reduced, or temporarily or permanently discontinued following the guidelines specified in the sections below.

---

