**TABLE 1B: INTERVENTIONS FOR NEUTROPENIA AND THROMBOCYTOPENIA BY NCI CTCAE GRADE**

Adverse Event	Grade				
	1	2	3	4	5
Neutrophils (ANC)	None	None	Interrupt pomalidomide treatment, follow CBC weekly Resume pomalidomide when ANC is $>1.0 \times 10^9/L$ , at 1 mg/day less than previous dose*	Interrupt pomalidomide treatment, proceed as for Grade 3	Off study
Platelets (thrombocytopenia)	None	None	Interrupt pomalidomide treatment, follow CBC weekly Resume pomalidomide when platelets are $>0.5 \times 10^9/L$ , at 1 mg/day less than previous dose	Off study drug permanently	Off study

\* For Grade 3 neutropenias in which the ANC is  $>0.8 \times 10^9/L$ , patient may remain on the same dose of drug for up to 1 week at which time a repeat CBC should be obtained. If the ANC is persistently less than  $1.0 \times 10^9/L$ , study drug should be discontinued until recovery of the ANC to  $>1.5 \times 10^9/L$  and the patient then restarted on the next lower dose.

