#### 6.1.8.6 FATIGUE

Fatigue may be observed in some patients. This may be difficult to separate from fatigue due to underlying HHT/anemia. For fatigue of CTCAE Grade 3 or higher ([https://ctep.cancer.gov/protocoldevelopment/electronic\\_applications/ctc.htm](https://ctep.cancer.gov/protocoldevelopment/electronic_applications/ctc.htm), version 4.0), pomalidomide may be stopped for 1-2 weeks at the investigator's discretion and then resumed at a dose of 3 mg daily, or simply reduced to a dose of 3 mg/daily. This dose may be continued for the remainder of the study or further reduced to 2 mg daily if fatigue is persistent.

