#### 6.1.8.10 HEPATOTOXICITY

Pomalidomide hepatotoxicity is rare. Elevations in bilirubin or transaminases > 3 times the baseline value should prompt temporary discontinuation of pomalidomide. Laboratory testing should be

performed two weeks after discontinuation to assure that abnormalities have resolved. If so, therapy may be resumed at a dose of 3 mg/day.

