#### 6.1.8.12 DOSE ADJUSTMENT FOR PERIPHERAL NEUROPATHY

Dose adjustments will be undertaken for peripheral motor neuropathy and peripheral sensory neuropathy as described in the tables below. Table 1C lists the NCI CTCAE Version 4.0 grading of adverse event severity for peripheral motor neuropathy and peripheral sensory neuropathy. Table 1D lists the intervention that will be used for each type of neuropathy according to NCI CTCAE grade.

TABLE 1C: NCI CTCAE FOR PERIPHERAL NEUROPATHY					
Adverse Event	Grade				
	1	2	3	4	5
Peripheral Motor Neuropathy	Asymptomatic; clinical or diagnostic observations only; intervention not indicated	Moderate symptoms; limiting instrumental ADL	Severe symptoms; limiting self care ADL; assistive device indicated	Life-threatening consequences; urgent intervention indicated	Death
Peripheral Sensory Neuropathy	Asymptomatic; clinical or diagnostic observations only; intervention not indicated	Moderate symptoms; limiting instrumental ADL	Severe symptoms; limiting self care ADL	Life-threatening consequences; urgent intervention indicated	Death

TABLE 1D: INTERVENTIONS FOR PERIPHERAL NEUROPATHY BY NCI CTCAE GRADE					
Adverse Event	Grade				
	1	2	3	4	5
Peripheral Motor Neuropathy	None	Hold Pomalidomide treatment for up to 4 weeks; restart at next lowest dose if symptoms resolve or improve to Grade 1	Off study drug permanently	Off study drug permanently	Off study
Peripheral Sensory Neuropathy	None	Hold Pomalidomide treatment for up to 4 weeks; restart at next lowest dose if symptoms resolve or improve to Grade 1	Off study drug permanently	Off study drug permanently	Off study

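### The fixed 3 mg/day restart after renal toxicity above Grade 1 (directed) or hepatotoxicity (permitted) is a reduction only from 4 mg; read literally, it repeats 3 mg and raises 2 mg by half

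*Protocol*

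**What the plan says.** Treatment starts at 4 mg/day (Protocol 6.1.7). Two lower strengths exist: "Capsules of 3.0 and 2.0 mg pomalidomide or matching placebo will also be provided for patients who experience hematologic toxicity, fatigue or muscle cramping" (6.1.2). Nothing below 2 mg is supplied.

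Two sections fix the dose at which drug is restarted after an organ toxicity:

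- **Renal, above Grade 1 (6.1.8.11).** Drug is withheld until the abnormality has resolved, and then "pomalidomide will then be reintroduced at a dose of 3.0 mg/day". This is a direction.
- **Hepatic (6.1.8.10).** If laboratory tests two weeks after stopping show resolution, "therapy may be resumed at a dose of 3 mg/day". This is a permission.

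Neither sentence mentions the dose at onset, and neither mentions 2 mg.

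The opening of 6.1.8 frames all of these rules: "Study drug dose may be reduced, or temporarily or permanently discontinued". Two other rules in the section depend on the dose in use. Table 1B restarts after cytopenia "at 1 mg/day less than previous dose", and Table 1D says to "restart at next lowest dose if symptoms resolve or improve to Grade 1" after neuropathy.

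**The concern.** A restart dose after drug-related organ toxicity should be no higher than the dose on which the toxicity occurred, and normally lower. A fixed 3 mg/day achieves this only for someone still on the starting dose.

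The protocol itself provides the other starting points. A participant can be on 3 or 2 mg through Table 1B, Table 1D, the fatigue rule (6.1.8.6), the cramping rule (6.1.8.8) or the general stepwise reduction (6.1.7). Section 6.1.8.3 names hematologic toxicity as the drug's main toxicity, so earlier reductions are foreseeable.

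The literal restart can also undo an earlier safety reduction. Suppose Grade 3 neutropenia occurs at 4 mg and again at 3 mg, so that Table 1B brings the participant to 2 mg. If a renal event above Grade 1 then occurs and resolves, 6.1.8.11 directs 3 mg. That is above the dose at the renal event, and it is the dose at which neutropenia recurred. What is at stake is participant safety in a few possible cases.

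**Working it through.** The plan states no figure to reproduce. The check applies the restart wording to each dose a participant may be taking, then sizes the group on stated assumptions.

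**1. Dose change.** Inputs: doses of 4, 3 and 2 mg/day (6.1.2, 6.1.7), a 28-day cycle (6.1.5), and a restart at 3 mg/day (6.1.8.10, 6.1.8.11). Formula: (restart dose − dose at onset) / dose at onset.

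| Dose at onset | Per cycle | Fixed 3 mg restart | Next-lower-dose restart |
|---|---|---|---|
| 4 mg | 4 × 28 = 112 mg | (3 − 4)/4 = −25%, to 84 mg | 4 to 3 mg, −25% |
| 3 mg | 3 × 28 = 84 mg | (3 − 3)/3 = 0%, stays 84 mg | 3 to 2 mg, (56 − 84)/84 = −33% |
| 2 mg | 2 × 28 = 56 mg | (3 − 2)/2 = +50%, to 84 mg | no lower dose supplied |

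The two rules agree only in the first row.

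**2. How many participants.** The protocol calls both toxicities rare and gives no rates, so every percentage here is an assumption. Assumed: 2–10% of the 106 pomalidomide participants are on 2 mg, 8–20% are on 3 mg, and each of the two events (renal above Grade 1, hepatic) occurs in 1–3% whatever the dose.

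- On 2 mg: 106 × 0.02 = 2.12 to 106 × 0.10 = 10.6.
- Directed increase (renal above Grade 1, on 2 mg): 2.12 × 0.01 = 0.02 to 10.6 × 0.03 = 0.32.
- Permitted increase (hepatic, on 2 mg): the same, 0.02 to 0.32.
- On 3 mg: 106 × 0.08 = 8.48 to 106 × 0.20 = 21.2.
- Restart without reduction (either event, on 3 mg): 8.48 × 0.02 = 0.17 to 21.2 × 0.06 = 1.27.

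**3. Do other provisions override the restart dose?**

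- Section 6.1.7 lets the site PI step down to 3 or 2 mg for adverse events that cannot otherwise be managed. It is discretionary and does not amend the specific restart sentence.
- Section 6.1.8.4 lets the investigator hold drug and resume when that seems safe. It governs whether and when to resume, not at what dose.
- Both organ-toxicity sections require resolution first. Resolution is a reason to restart, not a reason to restart at a higher dose.

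A site that restarted at 2 mg after higher-grade renal toxicity would be acting sensibly, but against a direction in 6.1.8.11.

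**The case against.** The strongest reply is that the 50% increase appears only if one sentence is read apart from the rest. The general dosing statements (the protocol summary, 6.1.7 and the opening of 6.1.8) provide only for moving down, and no other section authorises going back up. The assigned dose is 4 mg, so 3 mg reads naturally as the first step from it. The hepatic restart is optional, resolution is required, and an investigator may hold the drug. This is largely right about intent, and it is why the point is a wording correction. It does not change what the renal sentence directs for someone on 2 mg.

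A reader might also infer more than the documents support:

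- **That the Grade 1 renal rule has the same defect.** It says "If these abnormalities are confirmed, the pomalidomide dose should be reduced to 3 mg/day". This cannot raise a dose, and Tables 1B and 1D prescribe no action at all at Grade 1. Remaining on 3 mg after a Grade 1 creatinine rise is therefore no less cautious than those rules.
- **That the fatigue rule has it too.** The drug may be stopped "and then resumed at a dose of 3 mg daily", but that rule is wholly permissive, offers simple reduction instead, and adds a further step to 2 mg.
- **That Tables 1B and 1D are complete models.** They are useful comparators only because they are relative to the dose in use. They too have no floor: one step below 2 mg is a dose that is not supplied.
- **That the protocol intends re-escalation.** Nothing supports this.

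**Conclusion.** The point holds for two sentences: the directed restart in 6.1.8.11 after renal toxicity above Grade 1, and the permitted restart in 6.1.8.10 after hepatotoxicity. Applied as written, they give no reduction at 3 mg and a 50% increase at 2 mg, contrary to the framework of 6.1.8. This part follows from the text alone.

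The number of participants affected does not. It rests on assumed rates for both prior reductions and events, and the expected number with a directed increase is well below one. Sample size, power, alpha and the planned analyses are untouched. It is a low-priority safety wording point, worth correcting because the correct wording is easy to supply.

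**What to change.** In the two restart sentences, replace the fixed 3 mg/day with: *the next lower supplied dose than that at onset (4 to 3, 3 to 2 mg/day), never above the dose at onset*. Add: *for an event at 2 mg/day, stop study drug unless the investigator judges that resuming 2 mg is safe*. The Grade 1 renal rule, the fatigue rule and Tables 1B and 1D need no change for this point.

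The costs are:

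- **Wording.** A few lines in an amendment.
- **Extra reductions.** Participants on 3 mg with either event would restart at 2 mg: 0.17 to 1.27 pomalidomide participants on the assumed rates, each losing a third of the dose.
- **Extra stops.** If every event at 2 mg led to a stop, 2 × 0.02 = 0.04 to 2 × 0.32 = 0.64 pomalidomide participants. Applying the same rates to all 159 randomized participants, since placebo participants follow the same blinded rules, gives 159 × 0.02 × 0.02 = 0.06 to 159 × 0.10 × 0.06 = 0.95.
- **Lost data.** Under 7.3.5, a participant who stops before cycle 6 has only the current-cycle visit and the end-of-study visit, so each such stop would lose the week 24 ESS. The expected loss is below one participant.

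SAP Appendix 3 counts 127 of 159 participants as through week 24 or discontinued at the May 2023 snapshot. If dosing has ended, the correction serves any reuse of this protocol text.

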#### 6.1.8.12 DOSE ADJUSTMENT FOR PERIPHERAL NEUROPATHY

Dose adjustments will be undertaken for peripheral motor neuropathy and peripheral sensory neuropathy as described in the tables below. Table 1C lists the NCI CTCAE Version 4.0 grading of adverse event severity for peripheral motor neuropathy and peripheral sensory neuropathy. Table 1D lists the intervention that will be used for each type of neuropathy according to NCI CTCAE grade.

TABLE 1C: NCI CTCAE FOR PERIPHERAL NEUROPATHY					
Adverse Event	Grade				
	1	2	3	4	5
Peripheral Motor Neuropathy	Asymptomatic; clinical or diagnostic observations only; intervention not indicated	Moderate symptoms; limiting instrumental ADL	Severe symptoms; limiting self care ADL; assistive device indicated	Life-threatening consequences; urgent intervention indicated	Death
Peripheral Sensory Neuropathy	Asymptomatic; clinical or diagnostic observations only; intervention not indicated	Moderate symptoms; limiting instrumental ADL	Severe symptoms; limiting self care ADL	Life-threatening consequences; urgent intervention indicated	Death

TABLE 1D: INTERVENTIONS FOR PERIPHERAL NEUROPATHY BY NCI CTCAE GRADE					
Adverse Event	Grade				
	1	2	3	4	5
Peripheral Motor Neuropathy	None	Hold Pomalidomide treatment for up to 4 weeks; restart at next lowest dose if symptoms resolve or improve to Grade 1	Off study drug permanently	Off study drug permanently	Off study
Peripheral Sensory Neuropathy	None	Hold Pomalidomide treatment for up to 4 weeks; restart at next lowest dose if symptoms resolve or improve to Grade 1	Off study drug permanently	Off study drug permanently	Off study

#### 6.1.9 DURATION OF THERAPY

The duration of pomalidomide therapy will be 24 weeks.

#### 6.1.10 TRACKING OF DOSE

Only enough pomalidomide capsules for 1 cycle (i.e., 28 days) of therapy will be provided to the patient each cycle. Patients will be instructed to return empty bottles or unused capsules at each in-person visit.

Returned empty bottles or unused study drug will be disposed by the clinical site (according to site procedures) after documentation. If any study drug is lost or damaged, its disposition should be documented in the source documents.

#### 6.1.11 DRUG/DEVICE SPECIFIC CONSIDERATIONS

Pomalidomide (POMALYST®) or matching placebo will be provided to research subjects for the duration of their participation in this trial at no charge to them or their insurance providers. Pomalidomide will be provided in accordance with the POMALYST REMS™ program. Per the standard POMALYST REMS™ program requirements, all physicians who prescribe pomalidomide for research subjects enrolled into this trial, and all research subjects enrolled into this trial, must be registered in and must comply with all requirements of the POMALYST REMS™ program.

#### 6.2 STUDY AGENT ACCOUNTABILITY PROCEDURES

Patients will be instructed to return all empty bottles or unused capsules at each of the 6 treatment visits. Pill counts will be conducted at every treatment visit to determine compliance.

2. How long did your nose bleeding episodes *TYPICALLY* last during the past 4 weeks?
  - Less than 1 minute [0]
  - 1 to 5 minutes [1]
  - 6 to 15 minutes [2]
  - 16 to 30 minutes [3]
  - More than 30 minutes [4]
3. How would you describe your *TYPICAL* nose bleeding intensity during the past 4 weeks?
  - Not Typically Gushing or Pouring [0]
  - Typically Gushing or Pouring [1]
4. Have you sought medical attention for your nose bleeding during the past 4 weeks?
  - No [0]
  - Yes [1]
5. Are you anemic (low blood counts) currently?
  - No [0]
  - Yes [1]
  - I don't know [2]
6. Have you received a red blood cell transfusion *SPECIFICALLY* for nose bleeding during the past 4 weeks?
  - No [0]
  - Yes [1]

**Table 2:** Questions comprising the epistaxis severity score.

Question	Response	Multiplied by		Coefficient	Result
1	Less than monthly	0	X	0.14 (0.70 Den)	
	Once per month	1			
	Once per week	2			
	Several per week	3			
	Once per day	4			
	Several per day	5			
2	<1 minute	0	X	0.25 (1.00 Den)	
	1-5 minutes	1			
	6-15 minutes	2			
	16-30 minutes	3			
	>30 minutes	4			
3	No	0	X	0.25 (0.25 Den)	
	Yes	1			
4	No	0	X	0.30 (0.30 Den)	
	Yes	1			
5	No	0	X	0.20 (0.20 Den)	
	Yes	1			
	I don't know	Drop			
6	No	0	X	0.31 (0.31 Den)	
	Yes	1			
Total				Denominator (Sum Den)	Raw Score
Normalized HHT-EES		=	[Raw Score Denominator (2.76)]	X 10	

**Table 3:** Sample table for calculation of the ESS.

#### 7.1.1.2 EPISTAXIS DURATION

In addition to the ESS, subjects will be asked to determine the total duration of epistaxis at several four week intervals during the study (4 weeks prior to baseline, and between weeks 8-12 (C2-C3), 20-24 (C5-C6), and 4 weeks after treatment discontinuation (C6-EOS)) using an electronic diary with paper backup. The total weekly epistaxis duration averaged over these four week intervals will be assessed as a secondary endpoint as described in sections 4.2.2 and 10.2.

#### 7.1.1.3 QUALITY OF LIFE INSTRUMENTS

QOL instruments will be performed at baseline, after 12 and 24 weeks of treatment, and 4 weeks after the end of treatment. The QOL is assessed using three validated NIH instruments as well as the HHT-specific questionnaire developed during the design of this study (described in Section 2.1):

The three NIH instruments are:

1. **Neuro-QOL Satisfaction with Social Roles and Activities Short Form V1.1.** 8 questions. Total score is calculated as a T score using Neuro-QOL scoring engine.
2. **PROMIS Emotional Distress – Depression Short Form 8b V1.0.** 8 questions. Total score is calculated as a T score using PROMIS scoring engine.
3. **PROMIS Fatigue Short Form 6a V1.0.** 6 questions. Total score is calculated as a T score using PROMIS scoring engine.

The HHT-specific survey  (see Appendix 1) includes the following four questions:

1. How often in the past 4 weeks has an activity related to your work, school, or regularly scheduled commitments been **interrupted by a nose bleed?**
2. How often in the past 4 weeks has an activity with your partner, family, or friends been **interrupted by a nose bleed?**
3. How often in the past 4 weeks have you **avoided social activities** because you were **worried about having a nose bleed?**
4. How often in the past 4 weeks have you **had to miss** work, school, or regularly scheduled commitments because of **HHT related problems other than nosebleeds?**

A total score is calculated by summing the items 1-4 (each ranging from 0-4). The total score ranges from 0 (no limitations) to 16 (severe limitations). If any items are not answered, the total score will not be calculated.

#### 7.1.1.4 COUNSELING

Patients will be provided with their laboratory results and interpretation at each visit. Their symptoms will be reviewed and they will be counseled concerning the relationship of these symptoms, if any, to pomalidomide and/or HHT.

## 7.1.2 STANDARD OF CARE STUDY PROCEDURES

### 7.1.2.1 MEDICAL HISTORY

A full medical history will be taken during the screening visit. An interval history including questions to allow calculation of the ESS will be taken at all subsequent visits.

### 7.1.2.2 PHYSICAL EXAMINATION

A full physical examination including vital signs, examination of the nasal mucosa, examination of the heart, lungs, abdomen and extremities, as well as a brief neurologic examination with emphasis on peripheral neuropathy will be performed at screening, at month 3 of the treatment period, at the end of treatment (cycle 6) and at the end of study. A limited physical examination including vital signs, HEENT and cardiopulmonary examinations will be performed during all other visits. At remote visits, physical exam will be performed to the extent possible. If the screening visit is performed remotely, the baseline visit will include a full physical examination.

### 7.1.2.3 CONCOMITANT MEDICATION

Patients will be allowed to use any concomitant medications that they require except those listed in the exclusion criteria and section 7.6 Prohibited Medications, Treatments and Procedures. They may remain on HHT-directed medications other than those listed in the exclusion criteria if they were taking these when eligibility was determined. If they remain on such medications, they must remain on a stable dose during the study. Concomitant medications will be reviewed at screening, and at each study visit.

## 7.2 LABORATORY PROCEDURES/EVALUATIONS

### 7.2.1 CLINICAL LABORATORY EVALUATIONS

#### 7.2.1.1 STANDARD OF CARE LABORATORY STUDIES

##### **CBC**

A CBC with differential will be performed at the screening visit and at all other study visits. Hematologic toxicities of pomalidomide and their grading are discussed in Table 1A. The Hgb, WBC, absolute neutrophil count (ANC) and platelet counts at all study visits will be recorded.

##### **Complete Metabolic Profile**

A complete metabolic profile including renal and liver function studies will be performed at screening, at the initiation of therapy, each month during pomalidomide therapy, and at the end of treatment. The ALT, AST, alkaline phosphatase, total bilirubin, creatinine and BUN at all study visits will be recorded.

### ***Iron Studies***

Ferritin, iron and total iron binding capacity (TIBC) (to determine iron saturation) will be obtained at screening, at the initiation of therapy, each month during treatment, at the end of treatment and at the end of the follow-up period.

### ***PT/INR (International Normalized Ratio) and Activated Partial Thromboplastin Time***

Hemostasis will be assessed by measuring the PT/INR and activated partial thromboplastin time (aPTT or PTT per local laboratory designation) tests. These two tests will only be done at screening and are not required at other study visits. For study entry, the INR should be  $\leq 1.4$  and aPTT should be within the normal range ( $\pm 2$  sec) per local laboratory guidelines (except for patients on a stable dose of warfarin or direct oral anticoagulants).

---

#### **7.2.1.2 NON-STANDARD OF CARE LABORATORY STUDIES**

##### ***Genetic Testing***

All patients who provided consent for genetic testing will undergo testing for at least the three primary genes associated with HHT (endoglin (ENG), ACVRL1 and SMAD4) if they have not had prior testing or if the results for these three genes are not available. Genetic testing will be performed at Ambry Genetics, Aliso Viejo, CA. Samples will be shipped to Ambry, who will determine whether genetic testing costs will be covered by the patient's health care insurer. If not, Ambry will perform genetic testing at a reduced rate that will be covered by this study.

